see Authentication). **Anovulation** (defined as a total of \leq 8 menses per year) and presence of **polycystic ovarian morphology** on transvaginal ultrasound as determined by a trained obstetrician/gynecologist ([name]), **obesity and IR** will be additional enrollment criteria for the AE-PCOS population. **Sex as a biological variable:** Only females will be used for these studies since AE-PCOS is a female-specific disorder.

Control subjects will be **obese, IR** women, with regular menses every 26-34 days. Subjects will be excluded if they have any symptoms of AE-PCOS subjects, including polycystic appearing ovaries (as determined by transvaginal ultrasound ([name])).

For Aim 1, 2 and 3: All subjects will be given urine collection containers to collect their overnight urine prior to visits 4,5 and 6.

For Aim 1, 2 and 3: All subjects will self administer Antagon injections for a total of 10 days. Subjects may be kept on Antagon for as long as 18 days if there is a challenge with experiment scheduling. Subjects will also ingest a testosterone pill for seven days. Subjects may also be kept on testosterone for up to 11 days with regard to scheduling issues.

For Aim 5: Subjects will participate in only one baseline study (Fig 7). We will recruit black and white women to participate in this study with AE-PCOS.

EXPERIMENTAL PROTOCOLS:

Aims 1 & 2. Study design (Fig 7) and Hormone administration (Fig 8): IR subjects with and without AE-PCOS will be randomly (MiniTab, © cleverbridge, Inc.) divided into two **Protocol** groups (4 groups total, n=18 each) to be tested 3 times each: **Protocol 1:** prior to GnRH antagonist (Day 1); GnRH antagonist (250 μ g/day in 0.5 ml normal saline, Days 3 and 10). **Protocol 2:** prior to GnRH antagonist (Day 1), GnRH antagonist alone (Day 3), GnRH antagonist + methyltestosterone (Day 10). In both Protocols, Day 1 in Controls occurs in the proliferative phase of the menstrual cycle (days 1-7, low hormone phase); GnRH suppression begins on days 26-28 of that cycle. Non-cycling women with AE-PCOS begin testing at their convenience.

*Women may take the Antagon pills for as long as 18 days. We allow this flexibility because of challenges with scheduling subjects. There is no increase in risk, and we do everything possible to avoid the rare instance where taking this drug needs to be extended. If the drug is extended, "day 10" procedures occur on the final day of "GnRH antagonist + methyltestosterone" administration.

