Figure 7. The Overall Plan for Human Studies
proposed in Aims 1 and 2. Studies to assess the baroreflex and renin angiotensin system (RAS) will be performed in the same protocol. Overnight (12 hour) urine will be collected on all subjects prior to these protocols.

[figure not shown]
[figure not shown]
[figure not shown]

Figure 8. Hormone

Aim 3. Study design (Fig 7a) and Hormone administration (Fig 8): IR subjects with and without AE-PCOS will be randomly (MiniTab, © cleverbridge, Inc.) divided into two Protocol groups (4 groups total, n=8 each) to be tested 3 times each: Protocol 1: prior to GnRH antagonist (Day 1); GnRH antagonist (250 µg/day in 0.5 ml normal saline, Days 3 and 10). Protocol 2: prior to GnRH antagonist (Day 1), GnRH antagonist alone (Day 3), GnRH antagonist + methyltestosterone (Day 10). In both Protocols, Day 1 in Controls occurs in the proliferative phase of the menstrual cycle (days 1-7, low hormone phase); GnRH suppression begins on days 26-28 of that cycle. Non-cycling women with AE-PCOS begin testing at their convenience.

Standard Preliminary Procedures for all Protocols. The subjects maintain their normal diet and activity for three days prior to any experimental protocol and avoid alcohol and caffeine for 12 hrs prior to arriving at the laboratory. The subjects will arrive at the laboratory at 0800 having fasted for 8 hrs prior to the cardiovascular experiments. They will eat their normal diet for three days prior (see PROCEDURES) and drink water based on their body weight. On the morning of the experiment, we assess hydration from urine specific gravity (S.G.) of the initial urine sample. If S.G.>1.020, the subjects will drink 5 ml/kg of water, followed by a 30 min control period until hydration is deemed sufficient (S.G. <1.020). On all days that subjects visit the laboratory, they will take a rapid Covid 19 test according to the directions of the test. The subject will take this test in a separate chamber. This test will involve putting a "q-tip" like swab in each nostril and rubbing in a circular motion ten times and then placing the swab into analysis fluid from the test kit. A member of our research team will observe the swabbing procedure and read the results of the test. If the test is positive, the subject will not proceed further with the experiment, and will be asked to leave the laboratory immediately and suggest contacting their personal physician. If the test is negative, we will proceed with the experiment.

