Aim 1: Statistical analyses: Univariate statistics [mean (SD)] will be generated on all study variables first, which will determine the normality or the heteroscedacity of the data. Data will be analyzed using SPSS 21 statistical software that includes calculations to compensate for missing data, and Prism (GraphPad) curve fitting software where appropriate. **Data analysis.** The slopes of the linear regressions for PI-SBP (cardiovagal baroreflex gain), PI-LBNP (integrated baroreflex gain), resting MSNA, slopes for MSNA-DBP (sympathetic baroreflex gain during Oxford and Valsalva), will be compared between treatment conditions (GnRH antagonist vs. GnRH antagonist+T and between groups (Control vs AE-PCOS) using a 2-way repeated measures ANOVA with supplemental *post hoc* testing with Tukey's HSD test. **Sample size.** The desired statistical test is two-sided, and we assume an alpha level of =0.01 to account for multiple comparisons (37). In our laboratory, we observed effect sizes (SD) of PI-SBP intercept (with n=4) of 0.39 (0.16), our most stringent variable. A sample size of 15 women per group will allow us \geq 80% statistical power ($1-\beta > 0.9$) to test within group comparisons, and this same sample size will allow $[1-\beta]=0.80$ to distinguish any between-group differences from chance alone (29). Due to the technical challenges of performing microneurography on multiple occasions in obese women, we overestimate and account for a $\sim 20\%$ failure rate, so we will recruit 18 subjects per group. **R&R:** **1) GnRH antagonist suppression/hormone add-back** is the gold standard and most reliable method to control sex hormones in young women. **2) Microneurography** is the gold standard and most sensitive and reliable available measure for MSNA. **3) Lower body negative pressure** and the **Modified Oxford Technique** are the gold standards and most sensitive and reliable

available measures of autonomic function in humans. We will report our methods and findings in detail and **full transparency** to permit others to reproduce and extend our findings. **Sex as a biological variable:** Only women are included in these studies because AE-PCOS is a female-specific disorder.

Aim 2: Statistical analyses: We use ANOVA as described in Protocols 1. **Sample Size** is based on calculations in Aim 1, as the Aim 1 variables are the more stringent.

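### The plan names no baseline-adjusted test of the randomised Day 10 comparison (antagonist versus antagonist plus testosterone), although each woman is measured twice before testosterone

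*Combined protocol and SAP*

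**What the plan says.** V.3 (Experimental Protocols, Aims 1 & 2) randomises women, with and without AE-PCOS, to two Protocols of 18 per cell, each woman tested three times. The testosterone Protocol runs "prior to GnRH antagonist (Day 1), GnRH antagonist alone (Day 3), GnRH antagonist + methyltestosterone (Day 10"; the other keeps the antagonist alone and is tested on the same days. Aim 3 repeats the design with women "divided into two Protocol groups (4 groups total, n=8 each) to be tested 3 times each".

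The analysis text appears in V.3 and again in V.12. The outcomes "will be compared between treatment conditions (GnRH antagonist vs. GnRH antagonist+T and between groups (Control vs AE-PCOS) using a 2-way repeated measures ANOVA", followed by Tukey's HSD. Aims 2 and 3 refer back to the same ANOVA and the same sample-size calculation. None of these places names a covariate, an ANCOVA or a change score.

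On sample size: "The desired statistical test is two-sided", and "we assume an alpha level of =0.01 to account for multiple comparisons (37"). The input is "we observed effect sizes (SD) of PI-SBP intercept (with n=4) of 0.39 (0.16), our most stringent variable". Fifteen women per group are said to give power above 0.9 within groups and 0.80 "to distinguish any between-group differences from chance alone (29").

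**The concern.** The Day 10 difference between Protocols is the only randomised, concurrently controlled test of hypotheses 1B and 2B, which concern androgen administration. Each woman brings two values of each outcome measured before testosterone, and the plan does not say how they are used.

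The cells are small. A chance difference between arms at Day 3 has a standard error of √(2/15) = 0.37 SD with 15 per arm and √(2/8) = 0.50 SD with 8. Raw Day 10 means carry forward whatever part of that imbalance persists. A change from Day 3 subtracts all of it, which is too much unless the visits are almost perfectly correlated. ANCOVA subtracts the part that the data support.

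The open specification also leaves several analyses available once the data are in: raw Day 10 means, change from Day 3, or an arm-by-visit interaction. They can give different answers.

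**Working it through.** **1. The plan's own figure.** Reading 0.39 (0.16) as a difference and SD gives d = 0.39/0.16 = 2.44. At two-sided alpha 0.01 with 15 per group, power exceeds 0.999, and 80% needs only 4 per group (normal) or 6 (t). So 15 for 0.80 does not follow. Reading 0.39 as d gives 6% power; as Cohen's f (d = 0.78), 29%. One variant comes close: f = 0.39, 60 women in two diagnostic groups, two visits and an assumed correlation of 0.5 give 79% between groups and above 99% within. It ignores the SD and concerns Control versus AE-PCOS, not the randomised arms.

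**2. Inputs for the illustration.** Alpha 0.01 two-sided and n = 15 per arm come from the plan. Assumed: 80% power for the unadjusted test, and a correlation ρ equal across all three visits. With 28 degrees of freedom, 80% power needs noncentrality 3.635, so d = 3.635/√(15/2) = 1.33.

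**3. Variance of the arm difference, in units of 2σ²/n.**
- Raw Day 10 means: 1
- Change from Day 3: 2(1−ρ)
- Day 10 minus the mean of Days 1 and 3: 1.5(1−ρ)
- ANCOVA on Day 3: (1−ρ²)·[1 + 1/(2n−4)], one degree of freedom fewer
- ANCOVA on Days 1 and 3: [1 − 2ρ²/(1+ρ)]·[1 + 2/(2n−5)], two fewer

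**4. Results at ρ = 0.5, n = 15.**
- Raw Day 10 means: 80%
- Change from Day 3: factor 1, so 80%
- ANCOVA on Day 3: 0.75 × 1.038 = 0.779; noncentrality 3.635/√0.779 = 4.12 on 27 df; 90%
- ANCOVA on Days 1 and 3: 0.667 × 1.08 = 0.72; noncentrality 4.28 on 26 df; 92%
- Day 10 minus the mean of Days 1 and 3: factor 0.75; 91%
- Three-visit repeated measures ANOVA, arm-by-visit F test (simulation): 87%

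Simulation with 20,000 trials per setting also gives 90% and 92% for the two ANCOVAs. Two-baseline ANCOVA therefore gains 12 points over the first two tests, but only 1 (92 − 91) to about 6 (92.4 − 86.7) over the three-visit forms.

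**5. Dependence on ρ, n = 15, ANCOVA on Day 3.** Each column fixes its own comparator at 80%.

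| ρ | versus raw Day 10 means | versus change from Day 3 |
|---|---|---|
| 0.3 | 82% | 94% |
| 0.5 | 90% | 90% |
| 0.7 | 98% | 85% |

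At ρ = 0.2 the gain over raw Day 10 means is nil.

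With raw Day 10 means fixed at 80%, two-baseline ANCOVA beats the three-visit interaction test by 17 points at ρ = 0.2, 13 at 0.3, 6 at 0.5 and under 1 at 0.7.

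**6. Aim 3 cells of 8, same d = 1.33.** Raw Day 10 means: noncentrality 1.327 × √4 = 2.65 on 14 df, power 41%. ANCOVA on Day 3 at ρ = 0.5: 0.75 × (1 + 1/12) = 0.8125; noncentrality 2.94 on 13 df; 50%. At ρ = 0.3 the factor is 0.91 × 1.083 = 0.99, which does not repay the lost degree of freedom, so there is no gain at 0.3 or below.

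**The case against.** The strongest reply is that a repeated measures ANOVA can already use the earlier visits. With three tests per woman, an arm-by-visit term compares Day 10 with Days 1 and 3, and at ρ = 0.5 that recovers most of what ANCOVA offers. This stands. A reader might infer that the plan never adjusts for baseline; the text does not show that. It shows a model left under-specified. The literal wording fits the three-visit reading poorly: it has two factors, condition and diagnosis, and Day 1 precedes the antagonist and so belongs to neither named condition. But the wording does not exclude it.

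A reader might also infer a loss of 10 points at the stated design. The documents do not support that either. The 0.80 is given for between-group differences, and the analysis sentence defines groups as Control versus AE-PCOS. The 18 per group does match the randomised cells, so the text is ambiguous, but no power is clearly tied to the Day 10 arm contrast. At the plan's own 0.39/0.16 every option has power near 100% and nothing is lost. At d = 0.78, power would go from 29% to between 38% and 42%.

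Two further points stand. Under randomisation, raw, change-score and repeated-measures contrasts are all unbiased, so this is about efficiency and pre-specification, not validity. And equal correlation across visits is doubtful: Day 1 is off drug and, in Controls, falls early in a cycle whose days 26-28 mark the start of suppression. Day 1 may therefore add less than the 92% suggests.

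**Conclusion.** The point holds as a gap in specification with an inexpensive remedy. The plan names no baseline-adjusted test of the Day 10 arm difference and does not identify the visits or term that would test it.

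The size is illustrative and rests on an assumed 80% power and an assumed correlation. With 15 per arm and ρ = 0.5, Day 3 ANCOVA adds about 10 points to a raw Day 10 or change-from-Day-3 test, and adding Day 1 makes it about 12. If the ANOVA were run on all three visits, the gain is about 1 to 6 points. Over ρ from 0.2 to 0.7, Day 3 ANCOVA gains from nothing to about 18 points over raw Day 10 means; against change from Day 3 it gains about 14 at 0.3 and 5 at 0.7. In Aim 3, the same effect at ρ = 0.5 goes from about 41% to 50%, so adjustment helps but does not rescue cells of 8.

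No bias or inflated error rate is shown. The case for acting is that one estimator is fixed in advance and information already collected is used.

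**What to change.** In V.3 and V.12, state that the testosterone effect is the difference between Protocols at Day 10, estimated by ANCOVA of the Day 10 value on the woman's Day 3 value (optionally also Day 1), with Protocol, diagnosis and Protocol × diagnosis as factors. Identify the arms by treatment, because the Research Design list in V.3 numbers them in the opposite order to the Protocols.

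Apply the same model to the Aim 2 hormones and to FMD in Aim 3, using Day 3 only in the small Aim 3 cells. Keep the repeated measures ANOVA for the Day 1 to Day 3 suppression contrast. Say how a woman with a failed Day 3 recording is handled, since the plan allows for about 20% microneurography failures.

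The cost is one or two degrees of freedom, already included in the ANCOVA figures above. No new visits, measurements or women are needed.

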Statistical analyses: We use ANOVA as described in Protocols 1 & 2 to test changes in blood pressure, FMD and baroceptor sensitivity. **Sample Size** is based on calculations in Aim 1, as the Aim 1 variables are the more stringent.

Aim 3: **We expect** AE-PCOS women will have greater resting blood pressure compared to Controls. **We expect** that women with AE-PCOS will have greater RAS hormonal responses to LBNP, reflecting greater RAS activation. **We expect** that testosterone suppression will reduce PRA, $S_{[ALD]}$, $S_{[ANG\ II]}$, PRA and $P_{[Renin]}$ response to LBNP, suggesting lower RAS activation in both Control and AE-PCOS. **We expect** that increasing $P_{[Tfree]}$ and FAI will increase RAS hormone response to LBNP, reflecting greater RAS activation responses to LBNP in AE-PCOS. **We expect** Flow Mediated Vasodilation to be lower in the women with AE-PCOS compared to control women, and we expect the suppression of testosterone to eliminate this difference. **We expect** that increasing $P_{[Tfree]}$ and FAI will increase FMD in women with AE-PCOS, with little impact on Controls. **We anticipate** that women with AE-PCOS will have lower baroreceptor sensitivity, compared to Controls, and that this will be improved with testosterone suppression. Finally, we expect increasing $P_{[Tfree]}$ and FAI will increase baroreflex sensitivity in women with AE-PCOS, with little impact on Controls. Since the methods to be used are in place in our laboratory, we don't anticipate any problems in performing the studies in this Aim.

Aim 4. We expect that testosterone will be suppressed similarly during elagolix and ganirelix treatments. We will use Cronbach's alpha as a measure of internal consistency or reliability (95).

Aim 5. We expect black women with AE-PCOS will have greater resting blood pressure compared to white women with AE-PCOS. We anticipate that slopes for MSNA-DBP will be greater in black women with AE-PCOS, indicating increased sympathetic BRS compared to white women with PCOS.

PROCEDURES

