Expected results, interpretation of data, limitations and anticipated problems: Based on our hypothesis, **we expect** that women with AE-PCOS will have greater RAS hormonal responses to LBNP, reflecting greater RAS activation. **We expect** that testosterone suppression will reduce PRA, $S_{[ALD]}$, $S_{[ANG\ II]}$, PRA and $P_{[Renin]}$ response to LBNP, suggesting lower RAS activation in both Control and AE-PCOS. **We expect** that increasing $P_{[Tfree]}$ and FAI will increase RAS hormone response to LBNP, reflecting greater RAS activation responses to LBNP in AE-PCOS. Since the methods to be used are in place in our laboratory, we don't anticipate any problems in performing the studies in this Aim.

Expected results, interpretation of data, limitations and anticipated problems: **We expect** AE-PCOS women will have greater resting MSNA compared to Controls. **We anticipate** that slopes for MSNA-DBP will be greater in AE-PCOS, indicating increased sympathetic BRS compared to Control. **We expect** that testosterone suppression will decrease slopes for MSNA-DBP in AE-PCOS, and testosterone administration will increase slopes for MSNA-DBP in both Control and AE-PCOS. In contrast, **we expect** reduced slopes of PI-SBP with modified Oxford and paced breathing, indicating decreased sympathetic and cardiovagal BRS in AE-PCOS women; **we expect** a steeper PI-SBP slope with androgen suppression, and a steeper PI-SBP slope with modified Oxford, as well as paced breathing and Valsalva in both groups. Since all methods to be used are in place in our laboratory, we don't anticipate any problems in performing the studies in this Aim.

Aim 3: Statistical analyses: We use ANOVA as described in Protocols 1. **Sample Size** is based on calculations in Aim 1, as the Aim 1 variables are the more stringent.

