Expected results, interpretation of data, limitations and anticipated problems: **We expect** AE-PCOS women will have greater resting blood pressure compared to Controls. **We expect** that women with AE-PCOS will have greater RAS hormonal responses to LBNP, reflecting greater RAS activation. **We expect** that testosterone suppression will reduce PRA, $S_{[ALD]}$, $S_{[ANG\ II]}$, PRA and $P_{[Renin]}$ response to LBNP, suggesting lower RAS activation in both Control and AE-PCOS. **We expect** that increasing $P_{[Tfree]}$ and FAI will increase RAS hormone response to LBNP, reflecting greater RAS activation responses to LBNP in AE-PCOS. **We expect** Flow Mediated Vasodilation to be lower in the women with AE-PCOS compared to control women, and we expect the suppression of testosterone to eliminate this difference. **We expect** that increasing $P_{[Tfree]}$ and FAI will increase FMD in women with AE-PCOS, with little impact on Controls. **We anticipate** that women with AE-PCOS will have lower baroreceptor sensitivity, compared to Controls, and that this will be improved with testosterone suppression. Finally, we expect increasing $P_{[Tfree]}$ and FAI will increase baroreflex sensitivity in women with AE-PCOS, with little impact on Controls. Since the methods to be used are in place in our laboratory, we don't anticipate any problems in performing the studies in this Aim.

Aim 4. **We expect** that testosterone will be suppressed similarly during elagolix and ganirelix treatments. We will use Cronbach's alpha as a measure of internal consistency or reliability (95).

SECTION VI: RESEARCH INVOLVING DRUGS, BIOLOGICS, RADIOTRACERS, PLACEBOS AND DEVICES

If this section (or one of its parts, A or B) is not applicable, state N/A and delete the rest of the section.

A. DRUGS, BIOLOGICS and RADIOTRACERS

1. **Identification of Drug, Biologic or Radiotracer:** What is (are) the **name(s)** of the drug(s) biologic(s) or radiotracer(s) being used? Identify whether FDA approval has been granted and for what indication(s).

Antagon and **Cetrotide** are FDA-approved for women undergoing in vitro fertilization and have been approved for use in HIC protocols 10294, 12676, 25890 and 26534 (women with PCOS). **Elagolix** is FDA-approved for women undergoing in vitro fertilization.

Methyl testosterone is FDA approved for use in women at a higher dose (100 mg) to treat acquired, generalized hypoactive sexual desire disorder (HSDD) in premenopausal women.

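### Aim 3 expects an FMD gap to be eliminated and Controls to respond little to testosterone, but nothing in the planned analysis can show that a gap is absent or an effect small

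*Combined protocol and SAP*

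**What the plan says.** The Aim 3 expected results appear in Section V.3 (Research Plan) and again in Section V.12 (Statistical Considerations). FMD is expected to be lower in AE-PCOS than in Controls, and "we expect the suppression of testosterone to eliminate this difference". Raising testosterone "will increase FMD in women with AE-PCOS, with little impact on Controls", and likewise "will increase baroreflex sensitivity in women with AE-PCOS, with little impact on Controls".

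For analysis, the Aim 3 text refers back to Aim 1: "We use ANOVA as described in Protocols 1". Section V.3 adds that the purpose is "to test changes in blood pressure, FMD and baroceptor sensitivity". The Aim 1 text compares treatment conditions and diagnosis groups "using a 2-way repeated measures ANOVA with supplemental" Tukey post hoc testing. It gives the treatment conditions as antagonist alone versus antagonist plus testosterone. The sample-size text is two-sided and says "we assume an alpha level of =0.01 to account for multiple comparisons".

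The Aim 3 design has 16 women per diagnosis, "divided into two Protocol groups (4 groups total, n=8 each) to be tested 3 times each". Day 1 precedes suppression. On Day 3 every woman is on antagonist alone. On Day 10 only Protocol 2 has testosterone added.

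No equivalence margin, equivalence test or confidence-interval criterion is given. Nor is any FMD effect size or SD.

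**The concern.** Each expectation contains a statement of no difference, or of a negligible one. An ANOVA with pairwise follow-up tests is built to detect differences. A non-significant result from it does not show that a difference is absent, least of all with 16 or 8 women per group.

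The suppression claim concerns how the AE-PCOS versus Control gap changes from Day 1 to Day 3. The treatment factor described for the ANOVA leaves Day 1 out, so the contrast that bears on this claim is not specified. Pairwise tests at each day would then invite two weak readings: that the gap was eliminated because Day 3 is not significant, and that testosterone acts only in AE-PCOS because the Control change is not significant.

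Aim 3's argument is that androgen excess drives endothelial dysfunction and that removing it restores function. If those readings were adopted, low power would count in favour of that argument. A gap that suppression left untouched could look closed, and a testosterone response shared by both groups could look specific to AE-PCOS.

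**Working it through.** **The plan's own figure.** No power is stated for Aim 3 or FMD. Aim 3 defers to Aim 1: 15 per group, alpha 0.01 two-sided, effect 0.39 (SD 0.16), power 0.80 between groups and above 0.9 within. Taking d = 0.39/0.16 = 2.44 gives power of about 1.00 at 15 per group. Taking d = 0.39 gives 0.06 between groups and 0.11 paired. Neither reproduces the stated figures. Reading 0.39 as an ANOVA f, with three measures and correlation 0.3, gives 0.80 (four groups of 15) and 0.91 (30 women in all), but the documents state neither the f nor the correlation. The point below does not depend on this.

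**Inputs.** From the documents: 16 versus 16 on Days 1 and 3, 8 Controls receiving testosterone, alpha 0.01 two-sided (0.05 shown for comparison). Assumed: effects of 0.5, 0.8 and 1.0 SD, and a within-woman correlation of 0.7 (range 0.5 to 0.85).

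**1. Missing a residual gap on Day 3.** Two-sample t, noncentrality d × √(n/2), 30 df. For d = 0.5: 0.5 × √8 = 1.41.

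| True gap | Missed at 0.01 | Missed at 0.05 |
|---|---|---|
| 0.5 SD | 89% | 72% |
| 0.8 SD | 67% | 41% |

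For 80% power the gap must be 1.28 SD at 0.01, or 1.02 SD at 0.05. Tukey at familywise 0.05 over 4 to 6 means misses a 0.5-SD gap about 88% to 93% of the time, so it is not always harsher than unadjusted 0.01.

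**2. Missing a testosterone effect in 8 Controls.** Paired t, noncentrality dz × √n, 7 df, with dz in SDs of the change.

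| True change | Missed at 0.01 | Missed at 0.05 |
|---|---|---|
| 0.5 SD | 93% | 77% |
| 1.0 SD | 65% | 32% |

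If both groups respond equally by 1.0 SD, the pattern of significance in AE-PCOS but not in Controls has probability 0.348 × 0.652 = 23% at alpha 0.01.

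**3. Suppression leaves the gap unchanged.** Simulated bivariate normal Day 1 and Day 3 values with a constant gap, 16 versus 16, alpha 0.01. Share of all trials with Day 1 significant and Day 3 not:

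| Gap | Correlation 0.7 |
|---|---|
| 0.5 SD | about 6% |
| 0.8 SD | about 12% |
| 1.0 SD | about 13% |

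Over correlations 0.5 to 0.85 and gaps 0.5 to 1.0 SD the range is 4% to 17%. The between-group difference in the Day 1 to Day 3 change rejects in 1% of the same trials.

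**4. Power of the right contrasts, alpha 0.01.** The SD of the change is √(2(1 − 0.7)) = 0.775.
- Full removal of a 0.5-SD gap: 0.5/0.775 = 0.645, power about 20% (11% to 45% over correlations 0.5 to 0.85).
- Full removal of a 0.8-SD gap: 0.8/0.775 = 1.03, power about 57%.
- Testosterone response differing by 1.0 SD of the change, 8 versus 8: noncentrality 1.0 × √(8/2) = 2.0, power about 21%.

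**5. Could equivalence be shown?** The 90% CI half-width for the Day 3 gap is 1.697 × √(2/16) = 0.60 SD. For the change in 8 Controls it is 0.67 SD of the change. Neither interval would normally fit inside an assumed margin of 0.5 SD, which would need about 70 per group for 80% power (one-sided 0.05, true difference zero).

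**The case against.** The attacked sentences are expectations, not decision rules. The formal Aim 3 hypothesis in the Statement of Purpose is directional: suppression improves endothelial function. It mentions neither an eliminated gap nor unresponsive Controls. A reader might infer that the investigators will declare elimination from a non-significant Day 3 test. No sentence in the documents says so, and that inference is not part of this point. What remains is that these sentences are the only text on how Aim 3 will be interpreted, and no criterion for absence accompanies them.

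A reader might also infer that the plan has no test at all of a changing gap. That goes too far. A two-way ANOVA of group by condition contains an interaction, and Section V.3 says the ANOVA is for testing changes. But the conditions it lists leave out Day 1, neither claim is tied to the interaction, and a significant interaction would show only that the gap or response differs.

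A third tempting reading is that an untouched gap would look eliminated about half the time. The 54% behind that (0.5-SD gap, correlation 0.7) holds only among trials already significant on Day 1, which are about 11% of trials. The joint chance is about 6%.

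The numbers also depend on choices the documents do not settle. The 0.5 SD is assumed, and alpha 0.01 appears only in the sample-size text. At 0.05 the miss rates fall to 72% and 77%. Finally, the proposed contrasts are themselves weak at these sizes. All of this stands, and it limits how strongly the point can be put.

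**Conclusion.** The point holds as a gap in the analysis plan that should be closed. Nothing planned for Aim 3 can show that the FMD gap is absent after suppression, or that testosterone has little effect in Controls. Pairwise non-significance would be poor evidence for either: a 0.5-SD effect is missed 89% (16 versus 16) and 93% (8 Controls) of the time at alpha 0.01, and 72% and 77% at 0.05. When suppression does nothing to the gap, reading significance day by day gives the misleading pattern in about 6% to 12% of trials (4% to 17% over the wider range of assumptions), against 1% for the diagnosis-by-day contrast.

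These figures rest on an assumed effect in SD units, an assumed correlation, normal data and complete follow-up. The 93% takes 0.5 SD of the within-woman change. If 0.5 SD is meant on the raw scale, the miss rate at 0.01 is 87% at correlation 0.7 and 56% at 0.9. The logical point needs none of these assumptions: a p-value above alpha does not establish absence at any alpha.

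**What to change.** In the Aim 3 analysis and expected-results text of Sections V.3 and V.12:

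1. Name the diagnosis-by-day contrast, the between-group difference in the Day 1 to Day 3 FMD change in all 16 versus 16 women, as the test of the suppression claim, with its 95% CI. Make Day 1 an explicit level of the condition factor. Replace *eliminate* with *reduce*.
2. Test AE-PCOS specificity of the testosterone response, for FMD and for baroreflex sensitivity, as the between-diagnosis difference in that response, with a CI. Report the Control effect with its own CI.
3. State that neither elimination of the gap nor lack of response in Controls will be concluded from a p-value above alpha.

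This costs wording and contrasts on data already planned, with no added women, visits or procedures. The downside is a narrower claim. Given the limited power of the contrasts and the 0.60-SD half-width of the 90% CI on Day 3, Aim 3 may be able to claim only a reduced gap, or may be inconclusive.
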